Hypothesis 2: Tamsulosin started five days preoperatively and taken until hospital discharge will significantly decrease the **duration** of postoperative urinary retention among neurosurgical patients undergoing decompressive laminectomy and/or spinal fusion procedures who experience this surgical complication compared to placebo. (Secondary Hypothesis) Hypothesis 3: Tamsulosin started five days preoperatively and taken until hospital discharge will significantly decrease the length of hospital stay among neurosurgical patients undergoing decompressive laminectomy and/or spinal fusion procedures compared to placebo. (Secondary Hypothesis)

Specific Aims:

- 1) To determine if the use of a uroselective alpha-1-adrenergic receptor antagonist during the perioperative period reduces the incidence and duration of POUR in neurosurgical patients undergoing decompressive laminectomy and/or spinal fusion.
- 2) To determine if reduced incidence and duration of POUR in this patient population will result in decreased length of hospital stay.

Experimental Design:

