The study design will be a prospective randomized controlled double-blinded clinical trial comparing a uroselective alpha-1-adrenergic receptor antagonist (tamsulosin, 0.4mg per day) with placebo in neurosurgical patients undergoing decompressive cervical or lumbar laminectomy and/or spinal fusion. The study population will consist of all neurosurgical patients undergoing decompressive laminectomy and/or spinal fusion at Mayo Clinic Rochester from the time of study initiation (early 2012) that meet inclusionary criteria, do not meet any exclusionary criteria, and give consent to enter the study. Patients that enter the study will be randomized to receive tamsulosin (treatment group) or placebo (control group). The primary outcome variable will be the incidence of POUR. Secondary outcome variables of interest will include duration of POUR and length of hospital stay. Additional variables (demographic factors, number of catheterizations, incidence of UTI, etc.) will also be collected for comparison of the homogeneity of the two groups with respect to known confounding factors and to analyze other outcomes of interest. Data on all outcome variables will be collected by the time of hospital discharge. Therefore, this study will require minimum follow up time and it is estimated that patients will actively be participating in the study for an average of 8-12 days. Patients and providers will be blinded to treatment assignment for the duration of the study.

Based on sample size calculations (see Analysis of the Data section below), it is estimated that 175 patients will need to be recruited into each group. The Department of Neurological Surgery at Mayo Clinic Rochester performs approximately 4000 major neurosurgical procedures per year, of which approximately half are spinal procedures. Of those, approximately 1000 cases should meet the surgical criteria for this study. Thus, it is estimated that a one-year time frame will provide sufficient time to recruit the necessary 350 patients and perform the study.

Methods:

Subject Recruitment and Retention:

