Secondary outcome variables include duration of POUR among those patients in which it occurs, number of intermittent catheterizations in those with urinary retention, incidence of UTI, and duration of hospital stay. Measurement of the duration of POUR will closely coincide with the methods for recording incidence of POUR as discussed above. The decision to use and the time of removal of indwelling urinary catheters will be left to the discretion of the primary neurosurgical team. Time of indwelling catheter removal after surgery will serve as time zero for beginning calculation of postoperative urinary retention duration if the patient later requires in and out straight catheterization. For patients without an indwelling catheter, the time patients leave the operating room will serve as time zero. Per the Urinary Retention Protocol (MC1156-214rev0610),

patients found to be experiencing POUR will be ordered to have a straight in and out catheterization performed by a member of the catheterization team after failure of noninvasive measures (e.g. trigger techniques, bladder massage, application of warmth, relaxed environment, privacy, ambulation) by the attending nursing staff member. Urinary retention will be considered resolved after two consecutive post-void residual urine scans have demonstrated less than 300 ml residual urine volume in a patient spontaneously voiding. The number of intermittent catheterizations is recorded in the EMR in accordance with the standardized protocol.

Patients suspicious of having a UTI based on signs and symptoms of urinary frequency, urgency, burning or pain will have a urine sample (via catheterization or spontaneous void) sent for routine urinalysis, gram stain, and culture/sensitivity by the nursing staff member responsible for the patient or the primary neurosurgical team, per instructions documented on the Urinary Retention Protocol (MC1156-214rev0610). Positive UTIs will be defined as positive gram stain in the presence of signs or symptoms of UTI, urine white blood cell count elevation, and positive culture of >10⁴ cfu/ml. Patients will be treated with the appropriate antibiotic based on culture sensitivity.

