All statistical analysis and report of results will be done in a confidential manner and no information linking individual patients with data from the study will be shared outside of the study. Every effort will be made to keep this data anonymous once it has been collected.

Analysis of the Data:

Baseline characteristics will be compared between the two study groups using a chi-squared or Fisher's Exact Test for categorical variables and multiple two sample t-tests for continuous variables. The primary outcome variable, incidence of POUR, as well as other categorical variables, such as incidence of UTI, will be analyzed using a chi-squared test or Fisher's Exact Test. Duration of POUR will be compared using a two sample non-paired t-test comparing means. An appropriate nonparametric test (e.g. Wilcoxon Rank Sum) will be used for non-normal appearing data as can be anticipated for length of hospital stay. Differences in the groups with respect to baseline variables will be used to construct a multiple linear regression model to control for potential confounding factors if necessary. Intention to treat analysis will be used for all comparisons between groups.

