The primary outcome measure of incidence of POUR was used to calculate sample size. Data gathered from multiple series suggests that postoperative urinary retention occurs in 2-69% of patients undergoing a variety of surgical procedures, with 38% occurring in neurosurgical patients undergoing simple decompressive spinal procedures. Using 20% (P2=0.20) as a conservative estimate of incidence, an effect size of 10% for the primary outcome variable (P1=0.10) would be clinically meaningful. Thus, P2-P1 = 0.10. Because incidence of urinary retention is a binary categorical variable, a chi-squared test can be used to compare groups. Based on a type I error rate of 0.05 (α), a type II error rate of 0.20 (β), and power of 0.80 the estimated sample sizes needed for each group are as follows. For a one sided type 1 error, there would need to be 175 subjects in each group. For a two-sided type 1 error there would need to be 219 subjects in each group. A one-sided test of significance is reasonable in this study because an increase in incidence of POUR experienced in the tamsulosin treated group is not anticipated and would not add additional useful information in terms of using tamsulosin for POUR. Thus, a reasonable estimate for sample size is 175 subjects in both the treatment and control groups. Furthermore, with 175 patients per arm, there would be 87% power to detect a 1 day difference in the duration of urinary retention and duration of hospital stay with a 1-sided significance level of 0.05 (this assumes an effect size for this secondary outcome variable of 0.30 [1 day difference in means/pooled standard deviation estimate of 3.33]).

Role in Project:

[name]: Co-Principalinvestigator for the study, responsible for study design, study implementation, data collection, reporting of adverse events, and manuscript preparation.

[name]: Co-investigator responsible for assisting in study implementation, data collection, and manuscript preparation.

[name]: Co-investigator responsible for IRB application, Informed Consent form, and pharmacy liaison.

[name]: Statistician responsible for overseeing statistics performed by the co-PI as part of the CTSA BERD program.

[name]: Member of the Office of Research and Regulatory support who will be assisting with the Investigational New Drug application and corresponding with the FDA.

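### Duration of POUR and catheterisation counts are defined only among patients who develop POUR, so that comparison is not protected by randomisation, and the stated 87% power for duration does not apply to it

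*Combined protocol and SAP*

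**What the plan says.** The restriction appears in two places. Hypothesis 2 concerns duration in patients "who experience this surgical complication compared to placebo". Outcome Measures lists "duration of POUR among those patients in which it occurs, number of intermittent catheterizations in those with urinary retention".

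Other places carry no such restriction. Specific Aim 1 refers to duration, and Experimental Design to duration and to number of catheterisations, without limiting either to patients with POUR. The sample-size paragraph of Analysis of the Data states that "with 175 patients per arm, there would be 87% power to detect a 1 day difference in the duration of urinary retention".

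On analysis, the plan says "Duration of POUR will be compared using a two sample non-paired t-test comparing means", with a nonparametric test for data that look non-normal. It names no test for catheterisation counts. It adds "Intention to treat analysis will be used for all comparisons between groups". For the primary outcome it assumes 20% POUR on control, and says that "an effect size of 10% for the primary outcome variable (P1=0.10) would be clinically meaningful".

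No section plans a comparison of retention days or catheterisations over all randomised patients. None describes the POUR-only comparison as conditional on a post-randomisation event.

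**The concern.** Randomisation makes the arms comparable as randomised. It does not make the patients who go on to develop POUR comparable. POUR is the primary outcome, and the treatment is expected to prevent about half of it. If the prevented episodes tend to be shorter or longer than the others, the remaining tamsulosin cases differ from the placebo cases for that reason alone. Mean duration could then differ between arms with no remaining episode changed. A drug that mainly prevents mild cases would appear to lengthen retention, and one that mainly prevents long cases would appear to shorten it.

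The intention-to-treat sentence does not resolve this. It fixes the arm in which a patient is counted, but it does not bring patients without POUR into an outcome defined only among those who have it.

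The analysis set also matters for power. A figure computed on every randomised patient cannot describe a test run on the minority with POUR. A non-significant duration result could be read as good evidence of no effect when the test had little chance of finding one.

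**Working it through.** **Inputs from Analysis of the Data:** 175 per arm; POUR 20% on control and 10% on tamsulosin; 38% as the neurosurgical reference incidence; difference 1 day; SD 3.33; one-sided 0.05. Effect size d = 1/3.33 = 0.300.

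**1. Reproduce the stated 87%.** The noncentrality is d / √(1/n₁ + 1/n₂). With 175 and 175 it is 0.3003 / √(2/175) = 2.81. The normal approximation gives Φ(2.81 − 1.645) = 0.878, and the noncentral t gives 0.877. Reducing n by 0.955 to allow for a Wilcoxon test gives 0.864. The stated figure is therefore right for 175 contributing patients per arm.

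**2. Apply it to the defined analysis set.** POUR patients: 175 × 0.20 = 35 and 175 × 0.10 = 17.5. The noncentrality is 0.3003 / √(1/35 + 1/17.5) = 0.3003 / 0.2928 = 1.03. The normal approximation gives 0.268 and the noncentral t 0.263, so power is about 26%. The difference detectable with 80% power is (1.645 + 0.842) × 3.33 × 0.2928 = 2.4 days.

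**3. Range over incidence (noncentral t; all treated-arm rates below are assumptions).**

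| Control / tamsulosin POUR | Patients | Power |
|---|---|---|
| 20% / 20% | 35 / 35 | 34% |
| 38% / 19% | 66.5 / 33.25 | 40% |
| 38% / 28% | 66.5 / 49 | 48% |
| 38% / 38% | 66.5 / 66.5 | 53% |

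No row approaches 87%.

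**4. What selection alone could do (illustration only).** The documents give no distribution of durations. Assume exponential durations with mean m, half of episodes prevented, a share s of those prevented coming from the shorter half, and remaining episodes unchanged. The mean is m(1 − ln 2) below the median and m(1 + ln 2) above it. The tamsulosin POUR-only mean is then (1 − s) × m(1 − ln 2) + s × m(1 + ln 2), and its difference from placebo is (s − 0.5) × 1.386m.

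With m = 3.33 (the plan's SD borrowed as a mean), the half-means are 1.02 and 5.64 days:

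- s = 60%: 0.4 × 1.02 + 0.6 × 5.64 = 3.79 against 3.33 days
- s = 50%: equal
- s = 40%: 0.6 × 1.02 + 0.4 × 5.64 = 2.87 against 3.33 days

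With m = 2, the gap at 40% or 60% is 0.1 × 2.77 = 0.28 days.

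A 1-day gap from selection alone needs 72% of prevented cases to come from the longer half at m = 3.33, and 86% at m = 2. Under the other distributions tried, the requirement is 75% (lognormal) and 98% (gamma).

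Simulated with m = 3.33, the POUR-only one-sided t-test shows benefit in about 1%, 4% and 12% of trials at s = 60%, 50% and 40%. The Wilcoxon test, which the plan would probably use for such skewed data, shows about 1%, 5% and 14%.

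**The case against.** **The restriction is a legitimate question.** Hypothesis 2 openly asks about patients who have the complication, and clinicians want to know how long an episode lasts. This stands, so the comparison should be kept. What it lacks is a statement that it is conditional, and an all-randomised companion.

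**The analysis set is not uniformly POUR-only.** Specific Aim 1, Experimental Design and the power statement carry no restriction. This also stands: the plan is inconsistent, with Hypothesis 2 and Outcome Measures the most explicit. But none of the unrestricted mentions sets out an all-patient analysis or says what value a patient without POUR would take. That catheterisation counts will be compared at all is inferred from their listing as a secondary outcome.

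**All-patient consequences are partly covered.** UTI incidence and length of stay are compared in everyone. A reader could also multiply incidence by mean duration to get retention days per randomised patient. That limits the impact, but it gives no interval or comparison for that quantity.

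**Stronger readings to avoid.** A reader might infer that the duration result will be biased in favour of tamsulosin. The documents do not support this. They say nothing about which episodes would be prevented, and preferential prevention of short episodes would count against the drug. The day differences above rest on assumed distributions. A mean of 3.33 days may also be too long: an exponential with that mean puts 22% of episodes beyond 5 days, which the protocol treats as prolonged. Nor does the point extend to the primary outcome, or show that the intention-to-treat principle is breached.

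**Conclusion.** The point holds for two secondary outcomes. The POUR-only comparisons of duration and catheterisations are conditional on an event that treatment is expected to change, so randomisation does not protect them and the plan does not say so. Whether bias would occur, in which direction and how large, cannot be determined from the documents. It is absent if prevention is unrelated to episode length.

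The power mismatch needs no assumption about bias. On the plan's own rates, SD and one-sided level, power for a 1-day difference in duration is about 26% rather than 87%. It is 40% to 53% at 38% control incidence with assumed treated-arm rates of 19% to 38%. The 87% remains usable for length of stay, which every patient contributes. Primary incidence and UTI incidence are unaffected.

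**What to change.** 1. In the sample-size paragraph of Analysis of the Data, restate the duration power for the POUR-only set (about 26% at 20% versus 10%, with the expected 35 and 17.5 patients), and keep 87% for length of stay only.
2. Keep the POUR-only comparison for Hypothesis 2. State in Analysis of the Data that it is conditional on a post-randomisation event and must be read with the incidence result.
3. In Outcome Measures and Analysis of the Data, add an all-randomised comparison of mean retention days and mean number of intermittent catheterisations. Set retention days to 0 for patients without POUR. Take catheterisations as recorded in the electronic medical record, 0 if none. Report the difference in means with a 95% bootstrap interval. With some 80% to 90% of retention-day values at zero, a rank test would largely repeat the incidence comparison.

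The cost is wording and one added analysis from data already collected; no planned test is removed. The all-patient measure has real limits. It mixes incidence with duration, does not isolate Hypothesis 2, and has low power for a pure duration effect. In simulation (exponential, mean 3.33 days, 20% incidence in both arms, episodes 30% shorter on tamsulosin), its 95% bootstrap interval shows benefit in 20% to 21% of trials. The POUR-only one-sided 0.05 test shows it in 41% to 43% (t-test) or about 35% (Wilcoxon). It therefore complements the POUR-only comparison and does not replace it.

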Pre-operative Post Void Residual Urine Volume:

A pre-operative post void residual (PVR) volume of urine will be obtained on all enrolled patients at their pre-operative clinic visit prior to beginning their drug assignment (tamsulosin or placebo). This will be measured using the same technique as will be performed during the post-operative period (see Outcome Measures below). This baseline PVR will help determine efficacy of the study drug as outcomes are measured. The residual will be done by a member of the study staff and patients will not be charged.

Outcome Measures:

The primary outcome measure will be the incidence of POUR. POUR will be defined as any of the following:

- 1) Estimated post-void residual (PVR) volume of urine greater than or equal to 300 mL.
- 2) Estimated retention urine volume of greater than or equal to 500 mL in patients unable to void.
- 3) Patients experiencing discomfort or distension and unable to void with lesser residual urine volume than 500 ml

Neurosurgical nursing staff currently follow the institutional Urinary Retention Protocol (MC1156-214rev0610.) This protocol includes an algorithm for both diagnosing postoperative urinary retention and its treatment. This protocol has been in use for all postoperative spine patients since 2003 and the most current version is based on the above definition of urinary retention. All residual volume of urine measurements will be made with a standard bladder scanner instrument that is currently in use on the neurosurgery wards. Presence or absence of urinary retention will be recorded in the electronic medical record (EMR) for later data retrieval and analysis.

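### The catheterisation count and duration clock miss retention managed by replacing an indwelling catheter, and the primary outcome has no 'not assessed' state for patients without a voiding trial

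*Combined protocol and SAP*

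**What the plan says.** All of the relevant text is in the combined protocol and SAP, mostly under Outcome Measures.

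- **Primary outcome.** POUR is met in any of three ways. The first is "Estimated post-void residual (PVR) volume of urine greater than or equal to 300 mL". The second is inability to void with at least 500 mL retained. The third is inability to void with discomfort or distension at a smaller volume. On recording: "Presence or absence of urinary retention will be recorded in the electronic medical record (EMR) for later data retrieval and analysis".
- **Catheterisation outcome.** It is the "number of intermittent catheterizations in those with urinary retention", and its source is stated as: "The number of intermittent catheterizations is recorded in the EMR in accordance with the standardized protocol".
- **Indwelling catheters.** "The decision to use and the time of removal of indwelling urinary catheters will be left to the discretion of the primary neurosurgical team". No rule covers re-insertion, and none covers a patient discharged with a catheter in place.
- **Duration, start.** "Time of indwelling catheter removal after surgery will serve as time zero for beginning calculation of postoperative urinary retention duration", with the condition "if the patient later requires in and out straight catheterization". Patients without an indwelling catheter start when they leave the operating room.
- **Duration, end.** Retention is resolved after "two consecutive post-void residual urine scans have demonstrated less than 300 ml residual urine volume in a patient spontaneously voiding".
- **Analysis.** Analysis of the Data specifies intention to treat for all group comparisons. Quality Control expects little missing data. Neither gives a rule for a missing or unassessable outcome.

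**The concern.** Two kinds of patient are not properly covered.

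The first has retention after catheter removal that is managed by putting an indwelling catheter back. The count looks only at in-and-out catheterisations, so this management is invisible to it. The start of the duration clock also depends on an in-and-out catheterisation having taken place. A between-arm difference in the count could then reflect which kind of catheter was used rather than how much retention there was.

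The second goes home without ever having attempted to void off the catheter. Each POUR criterion needs a post-void residual or an inability to void, so none can be met. Experimental Design has all outcome data collected by discharge, so nothing later can classify this patient. With only two states named, whoever abstracts or analyses the data must decide, without guidance, between absent, missing and excluded.

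At stake are the meaning of two secondary outcomes and some dilution of the primary comparison.

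**Working it through.** **1. Apply the definitions as written to four patients.**

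| Patient | Intermittent count | POUR | Duration start | Duration end |
|---|---|---|---|---|
| A: indwelling removed, cannot void and meets a criterion, one in-and-out, indwelling replaced, discharged with it | 1 | present | removal | none reached |
| B: indwelling removed, meets a criterion, four in-and-out, then voids with two low scans | 4 | present | removal | second low scan |
| C: indwelling removed, cannot void and is uncomfortable, indwelling replaced, no in-and-out | 0 | present (third criterion) | not defined | none while the catheter is in |
| D: first indwelling still in at discharge | none | no criterion can be met; state not specified | – | – |

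A and C have lower counts than B, yet B is the one who recovered. C is a POUR event with no time zero. A and any similar patient have no end time, and no censoring rule is given. D has no defined state.

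**2. Reproduce the plan's sample size** (Analysis of the Data). Inputs: 20% vs 10%, α 0.05, power 0.80; stated sizes 175 per arm one-sided and 219 two-sided.

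Uncorrected: n′ = [z_α√(2p̄q̄) + z_β√(p₁q₁ + p₂q₂)]² / d². With p̄ = 0.15 and d = 0.10, one-sided: (1.645 × 0.505 + 0.842 × 0.500)² / 0.01 ≈ 157. Two-sided gives 199.

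With continuity correction: n = (n′/4)[1 + √(1 + 4/(n′d))]² gives 177 one-sided and 219 two-sided. The plan's figures are therefore approximately those of the corrected formula, which is used below.

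**3. Dilution if unassessed patients are scored absent.** Let f be the share of would-be POUR events in each arm that is lost this way. It equals the share of patients affected if those patients have average risk. The rates become 0.20(1 − f) and 0.10(1 − f). The effective size is m = 175[1 − 1/(175d)]², and power = Φ{[d√m − 1.645√(2p̄q̄)] / √(p₁q₁ + p₂q₂)}.

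For f = 0: m = 155.6, and power = Φ{(0.10 × 12.47 − 0.831) / 0.500} = Φ(0.83) = 79.8%.

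| f (assumed) | Rates | Difference | m | Power, corrected | Power, uncorrected |
|---|---|---|---|---|---|
| 0 | 20% / 10% | 10 points | 155.6 | 79.8% | 83.8% |
| 5% | 19% / 9.5% | 9.5 points | 154.6 | 77.4% | 81.7% |
| 10% | 18% / 9% | 9 points | 153.5 | 74.8% | 79.6% |
| 20% | 16% / 8% | 8 points | 150.9 | 69.1% | 74.6% |

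**4. Compare with leaving those patients out.** Keep 20% vs 10% and reduce n to 175(1 − f), that is 166.25, 157.5 or 140. Then m = n[1 − 1/(0.10n)]² = 146.9, 138.1 or 120.7, and corrected power is 77.7%, 75.5% or 70.4%. Most of the power loss thus comes from not observing these patients. What scoring them absent adds is a shrunken absolute difference and a classification nobody can see.

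**The case against.** The case against is substantial, and much of it stands.

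- **Other endpoints do cover these patients.** A reader might infer that indwelling catheters fall outside every endpoint. They do not: removal sets time zero for duration, length of stay is recorded for everyone, and UTI is not restricted by catheter type.
- **Severe cases do not score best on the primary outcome.** A reader might infer this from patient A. But A is already a POUR event, and under the resolution rule A's retention stays unresolved. Only the count looks favourable.
- **The plan does not say that never-trialled patients are free of POUR.** That is a plausible default given two recorded states, but missing or excluded is equally open. Intention to treat fixes the comparison groups; it does not turn an unassessed outcome into a success.
- **Re-insertion may be uncommon.** The stated treatment of POUR is straight catheterisation. The discretion sentence can be read as concerning the perioperative catheter, and it does not mention re-insertion. A catheter left in may reflect surgical preference rather than retention.
- **Unseen documents may help.** The institutional retention protocol and the operations manual could address re-insertion. Endpoint scoring nonetheless belongs in the analysis plan.
- **The count is minor.** It belongs to none of the three hypotheses and has no power statement, although Outcome Measures does list it as a secondary outcome.
- **Blinding limits the harm.** Handling should be similar between arms, so the expected effect on the primary outcome is dilution. The documents show no mechanism for reversing the result.

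None of this removes the three gaps in the written rules: the count, the duration start, and the absence of a state for unassessed patients.

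**Conclusion.** The point holds as a gap in scoring rules. Followed literally, the count can rank a patient with unresolved retention below one who recovered, and the duration of some POUR events cannot be calculated. These two conclusions come from the definitions alone and need no assumed rate. How many patients they touch is unknown.

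For the primary outcome the conclusion is conditional. If patients without a voiding trial are scored absent, corrected power falls from about 80% to 77%, 75% or 69% for 5%, 10% or 20% affected. This assumes equal shares in both arms and average POUR risk among those affected. If retained catheters mostly reflect surgical preference in low-risk patients, the loss is smaller; if they concentrate in patients who would have had POUR, it is larger. The design starts at about 80% on the plan's own approximate method, so it has little room for either. The trial should settle these rules, but its primary result is not shown to be biased in either direction.

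**What to change.** Change scoring only, and leave catheter care as it is.

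1. **Count.** Replace it with the number of post-operative catheter re-insertions of either kind for retention, counted from first removal, or from leaving the operating room if no catheter was placed. Keep the intermittent count as a component. Also report days with any catheter after first removal.
2. **Duration.** For patients with an indwelling catheter, start the clock at first removal for any later POUR, whichever catheter is then used. Treat discharge with a catheter after POUR as unresolved, that is, censored at discharge. The planned t-test cannot take censored values, so name a time-to-event comparison for this outcome.
3. **Incidence.** Score re-insertion of either kind for failure to void as POUR. Record patients with no voiding trial before discharge as 'not assessed', report their number by arm, and run two sensitivity analyses, one counting them as absent and one as POUR. The second will label some surgeon-preference catheters as retention, so it is a bound and not the main analysis.

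The cost is a few more fields from the EMR already being abstracted, and a research endpoint that differs slightly from the nursing entry. The 'not assessed' category will not recover the lost power, but it makes the loss visible and keeps an arbitrary classification out of the primary result.
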